Cover Page for Clinical Trial Study

Official Title: Comparing the Effects of a Plush Toy Dog versus a Live Therapy Canine on
Prosocial Behavior and Emotional Regulation in Children with Autism Spectrum Disorder

NCT#: N/A

Date: March 13, 2025

Study Protocol

Clinical Study Description

The purpose of this project is to investigate the human-animal interaction (HAI) and bond (HAB) between a canine trained in therapy techniques or a canine plush toy and youth with autism spectrum disorder (ASD) during animal-assisted therapy (AAT) sessions. We seek to explore identified gaps in knowledge pertaining to AAT in pediatric ASD care management.

Specifically, we want to document human interaction between either a live canine or the plush toy canine during AAT sessions, evaluating behaviors observed during and after AAT sessions. Caregivers were given the option to enroll the child in the AAT study at the follow-up appointment after the diagnostic assessment was completed, or upon enrollment in the ASD program if the child had an ASD diagnosis. The study was conducted between June 2022 through August 2024. Each AAT study lasted between eight to 12 weeks, and caregivers had the option to re-enroll the child for the next study to continue addressing behavioral concerns.

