Participants were divided into two groups: one with a therapy canine and one with a plush toy dog. Therapy sessions lasted 30 to 45 minutes, depending on the age and ability of the participant. All participants, no matter their group, received the same therapeutic strategies, such as sensory integration therapy and seated activity with the therapist, who is a certified pediatric nurse practitioner. Sessions with the therapy canine started with five to 10 minutes of free play with the canine, followed by sensory integration therapy based on the child's identified sensory profile. Participants then entered the clinic room for 20 to 30 minutes of a seated activity in which the therapist who taught coping and socialization strategies to participants and caregivers. Sessions concluded with five minutes of play with the canine. Play activities include fetch, soccer, hide and seek, and puzzles. The canine was trained to lay under the table in the clinic room while the therapist was working with the participants. He would provide grounding, light pressure, and deep pressure therapy if the participant became anxious during the sessions. The seated work was recorded using two cameras to ensure visibility of the interactions between the participant and therapist, canine, and caregiver; participant vocalizations and verbalizations; and participant facial expressions. We used two human-animal ethograms to code behavior during sessions and two behavioral assessments to note behavior occurring after sessions. All sessions occurred in the clinic located on the university's campus. Demographic data including participant age, gender, race, ethnicity, referral source, prior medical diagnoses, age of ASD diagnosis, medications, and prior allied health, school, or psychological evaluations. The canine was certified as a therapy dog and service dog certified in 10 ASD service dog tasks at the time of the study. The canine was present during sessions to interact with children and assist them to practice and develop skills to address identified deficits in social-emotional and adaptive functioning, prosocial behavior, and emotional regulation. AAT sessions were recorded to code interactions at a later time.

Objectives

This study will address the following research questions:

1. How do children with autism ages 2 to 18 years interact with a live canine during AAT sessions?
2. How do children with autism ages 2 to 18 years interact with a toy plush dog during AAT sessions?

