3. Is there a difference in HAI in the live canine group and the toy plush dog group?
4. Is there a difference in prosocial behavior observed during AAT sessions between the live canine group and the toy plush dog group?
5. Is there a difference in behavior after AAT sessions between the live canine group and the toy plush dog group?

Design and Statistical Analysis Plan

We used two human-animal ethograms to investigate human-animal interaction and bonding occurring during AAT sessions. Prosocial behavior and emotional regulation demonstrated by participants outside of AAT sessions were assessed by two self-report questionnaires completed by caregivers. SPSS and Microsoft Excel were used to calculate the analysis. Descriptive statistics were utilized to compare prosocial behavior and emotional regulation occurring apart from AAT sessions between the two groups. Poisson analysis was conducted to examine human-animal bonding and human behavior occurring during AAT sessions. Independent *t*-tests were used to analyze the differences in human-animal interaction between the two groups. The homogeneity of the variance (HOV) assumption between two groups was checked using Levene's test for equality of variances in SPSS program before conducting the *t*-tests analysis. Results of *t*-tests with adjusted degrees of freedom value were reported if the HOV was violated. The null hypothesis was set to reflect no significant difference in HAI between groups for the independent *t*-tests; therefore, a significant difference in the human-animal interaction and human behaviors regarding the inclusion or exclusion of the canine could be confirmed if the *t*-test results reject the null hypothesis. Cohen's *d* was used to report the effect sizes of the independent *t*-tests; values up to 0.20 were interpreted as small, 0.50 as medium, and 0.80 as large effect sizes. Analysis of variance was used to assess differences between the two groups in prosocial behavior and emotional regulation occurring apart from AAT sessions.

Methods

Demographic data; past, family, and social histories; and prior therapy evaluations were collected during the initial consultation for enrollment into the ASD program. Additionally, pet ownership in the family home was included in the analysis.

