The 3-AAT Observation ethogram, adapted with permission from Johns Hopkins University, was used to code both canine and human interaction during AAT sessions. The revised ethogram appraises the frequency of six domains of human interaction (affection, play, care, communication, comfort, withdrawal) and 24 subdomains of human behavior that can occur in an AAT session. The ethogram assesses the frequency, intensity, and duration of the interactions between the canine and child. Frequency is measured by a tally count and duration is assessed by rounding either up or down to the nearest 30 second mark. Each interaction has a code for intensity from 0 (not intense) to 3 (the most intense), and the mode of the interaction was entered to run the analysis.

The Strengths and Difficulties Questionnaire (SDQ) is a 25-item tool developed to assess five domains: Emotional Problems, Conduct Problems, Hyperactivity, Peer Problems, and Prosocial. The SDQ is the most used instrument in measuring therapeutic effect of interventions within the emotional state in children and adolescents ages 2 to 18 years, demonstrating reliable internal

consistency and validity. The SDQ has two versions, one to be administered at the initiation of therapy and then a follow-up version that includes two additional questions examining the impact of the therapeutic intervention. Scores from four behavioral domains range from zero (“normal”) to 10 (“very high concerns”), while Prosocial domain scores are reversed so that 10 indicates “normal” behavior and zero signifies “very high concerns”. The SDQ also assesses the total, impact, internalizing, and externalizing scores to provide a complete overview of the child’s behavior during the past four weeks. Total scores are the sum of the behavior domains except the Prosocial domains and range from zero (normal) to 40 (very high). Impact scores range from zero (normal) to 10 (very high) and reflect overall distress and impairment interfering with daily social interactions. Internalizing scores reflect the Emotional Problems and Peer Problems domains, while Externalizing scores are the sum of the Conduct Problems and Hyperactivity domains. Both the Internalizing and Externalizing domain scores range from zero (normal) to 20 (very high). The initial SDQ was administered at the beginning of the study and the follow-up assessment was used subsequently every four weeks until the study concluded.

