Participants will be divided into 2 groups: one group will interact with the live canine while the other group will interact with a toy plush dog identical to the canine. [name] will use a variety of behavioral and developmental evaluations to identify concerns and provide strategies for home therapy to improve delays for both groups. The O'HAIRE Coding System and 3 AAT Observation ethogram will be used to observe and code human behavior during all sessions for both groups. Additionally, participants ages 8 years and older who are cognitively capable will be asked to self-report their emotional state before and after each AAT session using an 11-point Likert scale chart in the shape of a thermometer, with ranges from "no distress/totally relaxed" to "highest anxiety/stress that you've ever felt." A caregiver satisfaction and perspectives of AAT integration in therapy sessions will be assessed via surveys. Demographic data including participant age, gender, race/ethnicity, referral source, prior medical diagnoses, age of ASD or DD diagnosis, medications, and prior allied health or psychological therapies will be collected on all participants. [name] will incorporate AAT into the therapy sessions at the A4A clinic that are guided by the developmental, adaptive-functioning, and social/emotional assessments to target gross and fine motor skill, language, social, emotional, and adaptive-functioning development. Parents will be given handouts that are designed to address deficits identified by the assessments. The O'HAIRE Coding System will be used to observe and code human behavior during AAT sessions. Observable behaviors categories captured by the OHAIRE Coding System include Interactive Behaviors (Social Communication & Environmental Interaction), Emotional Display (Facial, Verbal), and Interfering Behaviors (Aggression, Overactivity, Isolation). The OHAIRE-V3 assessment will be used to calculate a human-animal bond score to quantify the interactions taking place between the pediatric participants and the animal. The ELAN Coding software will be used to achieve high inter-rater reliability through precise timing of observed interactions. The 3 AAT Observation ethogram assesses 26 canine behaviors during human-animal interactions. The ethogram is divided into three categories: affiliative indicators, moderate stress indicators, and high-stress indicators. All sessions will occur at the A4A clinic, which is located on campus in the Epley Center for Healthcare Professionals. The first interaction between the canine and the participant will focus on introducing the two and facilitating a bond through play, such as petting or brushing the canine, or throwing a ball. The canine will be present to interact with children as they are learning their skill for that week. For example, the canine will interact with the participant while the participant is learning a new skill, such as improvement in handwriting, and the participant will be able to interact and play with the canine if the participant focuses on completing the therapy assignment. Likewise, participants will earn points if they perform their therapy strategies at home and can use those points to interact and play with the canine at their next therapy session. Plush dog toys who look like the canine will be given to pediatric participants in both groups as incentive to perform their home therapies.

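### The ANOVA for out-of-session behaviour (question 5) names no score, visit, time factor, unit of analysis or role for the initial SDQ, and the readings it permits differ in their exposure to starting differences.

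*Combined protocol and SAP*

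**What the plan says.** The Design and Statistical Analysis Plan has two sentences on behaviour outside the sessions. One is descriptive: "Descriptive statistics were utilized to compare prosocial behavior and emotional regulation occurring apart from AAT sessions between the two groups". The other is the test: "Analysis of variance was used to assess differences between the two groups in prosocial behavior and emotional regulation occurring apart from AAT sessions". Neither names an instrument, score, visit, time factor, covariate or unit of analysis. The same section does give details for the t-tests (Levene's test, adjusted degrees of freedom, Cohen's d). The Methods section says that pet ownership was part of the analysis, without naming a model.

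The Methods section gives the SDQ schedule: "The initial SDQ was administered at the beginning of the study and the follow-up assessment was used subsequently every four weeks". The form describes "behavior during the past four weeks". It yields nine scores: five domains plus total, impact, internalizing and externalizing. On the total: "Total scores are the sum of the behavior domains except the Prosocial domains". The PANAS is weekly, and no form before the first session is described.

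On duration, the Clinical Study Description says: "Each AAT study lasted between eight to 12 weeks". This gives two or three follow-up SDQs, so three or four forms per child with the initial one. Re-enrolment in a later course is allowed.

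On group formation, the Clinical Study Description says: "Participants were divided into two groups: one with a therapy canine and one with a plush toy dog". The IRB questionnaire says: "Participants will be divided into 2 groups". Neither describes a method of allocation.

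**The concern.** Four analyses fit the sentence:

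1. Follow-up scores compared between groups without adjustment.
2. A group main effect averaged over all forms, including the initial one.
3. A group-by-time term, or change from the initial form.
4. A one-way ANOVA on child-visit rows treated as independent.

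They answer different questions and have different error rates. Under readings 1 and 2, a difference between the groups at the start can carry into the estimated canine effect. Reading 3 uses the initial form, but its result depends on whether a starting difference persists or fades. Reading 4 understates the standard error whatever the starting scores. A reader of a significant result cannot tell which of these applies.

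The choice of score is open too. The total leaves out the Prosocial domain, so it cannot stand for prosocial behaviour, and no SDQ score is labelled emotional regulation.

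**Working it through.** The documents give no power, SD or effect size for the SDQ, so there is no figure of the plan's own to reproduce. What follows is an illustration.

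**Inputs.** From the documents: three or four SDQ forms per child. Assumed: 75 per group (the IRB form lists 150 children but no split and no SDQ sample size) or 30 per group; unit SD; equal correlation ρ between forms of 0.3, 0.5 or 0.7; a starting difference d of 0.1 to 0.5 SD; no canine effect; two-sided 5% level.

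**Two cases.** Either d persists in full at follow-up, or it acts only through the initial score, so that the follow-up difference is ρd.

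**Formulas** (n per group, three forms for reading 2):

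| Method | Standard error | Bias, d persists | Bias, through initial score only |
|---|---|---|---|
| 1. Follow-up ANOVA | √(2/n) | d | ρd |
| 2. Main effect, all forms | √(2/n)·√((1+2ρ)/3) | d | (d+2ρd)/3 |
| 3. Change from initial | √(2/n)·√(2(1−ρ)) | 0 | −(1−ρ)d |
| ANCOVA on initial SDQ | about √(2/n)·√(1−ρ²) | (1−ρ)d | 0 |

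**Reading 1 over a range of d.** At n = 75 the standard error is √(2/75) = 0.163. If d persists, rejection is about 9%, 23%, 45% and 86% for d = 0.1, 0.2, 0.3 and 0.5.

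**All methods at d = 0.3, n = 75** (20,000 simulated trials per cell; noncentral-t figures agree to within about one percentage point). Ranges run over ρ = 0.3 to 0.7, in that order:

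| Method | d persists | Through initial score only |
|---|---|---|
| Follow-up ANOVA | about 45% | 8.5% to 25% |
| Main effect, three forms | 71% to 53% | 27% to 37% |
| Change from initial | 5% | 19% to 11% |
| ANCOVA | 26% to 12% | 5% |

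At 30 per group and d = 0.3, the persisting case gives about 21%, 34% to 25%, 5% and 13% to 8% for the same four methods.

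**ANCOVA is not a full cure.** If d = 0.3 persists, its remaining bias is (1−ρ)·0.3, which is 0.21 to 0.09 SD.

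**Reading 4.** With m rows per child and no starting difference, the variance is understated by the factor 1+(m−1)ρ, and the false-positive rate is 2[1−Φ(1.96/√(1+(m−1)ρ))]. For m = 2 and ρ = 0.3 the factor is 1.3 and the rate 8.6%. For m = 4 and ρ = 0.7 the factor is 3.1 and the rate 26.6%.

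**If allocation was random.** Readings 1 to 3 hold about 5%; reading 4 does not. Adjustment then buys precision only. The effective sample grows by 1/(1−ρ²), which is 1.10-, 1.33- or 1.96-fold over unadjusted follow-up.

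**The case against.** The strongest reply is that this is a reporting gap and not a demonstrated error. That stands. A repeated-measures ANOVA with a group-by-time term would fit the sentence and would use the initial SDQ. The mention of prosocial behaviour plausibly points to the SDQ Prosocial domain, although the plan never makes the link.

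The reply also says that the size rests on an assumed starting difference. That stands too, which is why a range is shown.

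Three stronger readings are tempting, and the documents do not support them:

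- A reader might infer that the groups differed at the start, or that allocation was not random. The text is silent on the method, which is not evidence against randomisation, and no initial scores are shown.
- A reader might infer that disagreement between ANCOVA and change from initial would reveal confounding. The two estimates differ by about (1−ρ) times the observed starting difference, whatever its cause. Under random allocation, a chance difference above 0.3 SD in either direction arises in about 7% of trials at 75 per group and 25% at 30 per group.
- A reader might take the initial SDQ as a score from before any care. The IRB questionnaire recruits children already managed by the program, and a re-enrolled child's new initial form follows an earlier course. The form precedes that AAT course and no more.

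Finally, the analysis text is in the past tense and the study is said to have run to August 2024, although the IRB record still lists it as open to enrolment. Overwriting the sentence would erase a record of what was done. That objection stands and shapes the fix.

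**Conclusion.** The concern holds as an underspecified analysis whose possible readings can lead to different conclusions. On two of the four readings a starting difference, if present, can be reported as a canine effect. On a third, false positives run at roughly 9% to 27% with no starting difference at all. Adjusting for the initial SDQ reduces the exposure but does not remove it, and it gains precision even if allocation was random.

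The percentages depend on the assumed group sizes, correlations and starting differences. They show how much the choice can matter, not what happened in this trial. The point should be fixed; confidence is medium, because the analysis actually run is not known. The calculation concerns the SDQ. The weekly PANAS has the same missing visit and time factor, but no form before the first session is documented for it.

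**What to change.** **State what was run:** the score, the visits, any time factor, the unit of analysis and how pet ownership entered. State how children were allocated.

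**Add a baseline-adjusted SDQ analysis,** labelled post hoc if outcomes are already known. Use first enrolments only, and one of two models:

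- ANCOVA of the score at one named visit on group and the initial SDQ. Week 8 is a reasonable choice, because 8- and 12-week courses both reach it.
- A mixed model over the follow-up visits with group, visit, group-by-visit, the initial SDQ as covariate and within-child correlation.

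**Name the measures.** The Prosocial score is the suggested headline for prosocial behaviour, with the other SDQ scores secondary. State which measure stands for emotional regulation.

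**Report alongside:** the initial SDQ by group, and the change-from-initial contrast as a sensitivity analysis, without treating disagreement as a test for confounding. Say that the initial SDQ precedes the AAT course but not necessarily all care, and that adjustment reduces but does not remove confounding.

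**PANAS:** model the weekly forms with within-child correlation. Adjust for the first form only if it was completed before or at the first session.

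**Cost.** No new data; rewritten text and a re-run in SPSS. Children without an initial SDQ are dropped or need imputation, re-enrolments are left out of this comparison, and the analysis may carry only post hoc weight.

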Data will be collected in the initial consultation form for the A4A clinic, through performing developmental, behavioral, social/emotional, and adaptive-functioning assessments, and with surveys. The following will be used to collect data: 1. A4A Intake form: all participants 2. Developmental screenings such as Ages and Stages Questionnaire- 3rd edition: 1 month to 5.5 years; Ages and Stages Questionnaire: Social/Emotional- 2nd edition: birth to age 6 years; Social and Emotional Assessment/ Measure: 2 to 66 months; Strengths and Difficulties Questionnaire: 3 to 16 years; Positive and Negative Affect Schedule: 9 to 14 years; Vineland- 3rd edition: 3 to 21 years; Social Responsiveness Scale- 2nd edition: 2.5 to 18 years; Standford-Binet IQ Test: 2 to 18 years; Autism Diagnostic Observation Scale-2: 18 months to adulthood; and Childhood Autism Rating Scale- 2: 2 years to adulthood. All AAT sessions will be recorded after receiving consent from families to retroactively code participant behavior during sessions with the OHAIRE and 3 AAT ethograms.

- **How will your data be stored? Include all that apply: electronically, on paper, audio and/or video recordings.**

Survey data will be stored in an Excel spreadsheet and Qualtrics, which is a HIPAA-secured software with which caregivers of youth with complete on a personal device (iPad, laptop, cellphone).

- **How will that data be kept secure?**

Data saved in the Excel spreadsheet will only be accessible by approved research staff and stored in [name] password protected laptop. Any hard-copy measures of documents will be stored in Drs. [name]'s locked office in a locked filing cabinet. Video files will be downloaded from camcorders directly to [name] secured laptop. Only authorized research personnel will have access to these files and only participant numbered IDs will be included on assessment documents. Participant identifying information and associated ID numbers will be stored in [name] lab in a password protected computer on a password protected document. [name] and approved research personnel will have access to participant ID information but will mainly utilize participant ID numbers. All video files will be downloaded to [name] computer within 24 hours and then immediately deleted from the camcorder device. Video files will be stored on a password-protected computer as password-protected documents.

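### The plan does not say where pet ownership enters the analysis, and the between-group test for human-animal interaction adjusts for nothing although random allocation is not described

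*Combined protocol and SAP*

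**What the plan says.** The first paragraph of Methods lists what was collected at the initial consultation and ends: "Additionally, pet ownership in the family home was included in the analysis". Nothing further is said about pet ownership.

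The Design and Statistical Analysis Plan names four kinds of analysis:

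- Descriptive statistics, for behaviour apart from sessions.
- A Poisson analysis: "Poisson analysis was conducted to examine human-animal bonding and human behavior occurring during AAT sessions".
- T-tests: "Independent *t*-tests were used to analyze the differences in human-animal interaction between the two groups". Levene's test is run first, and "Results of *t*-tests with adjusted degrees of freedom value were reported if the HOV was violated".
- ANOVA: "Analysis of variance was used to assess differences between the two groups in prosocial behavior and emotional regulation occurring apart from AAT sessions".

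No covariate, stratifier or second factor is named for any of them.

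The Clinical Study Description says that participants were divided into a live-dog group and a plush-dog group, and gives no method of division. The procedures answer in the IRB Questionnaire adds nothing on this. Age is among the demographic data collected, and the Objectives give the range as 2 to 18 years.

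**The concern.** An independent t-test compares two means and has no place for a third variable. The adjusted degrees of freedom deal with unequal variances, not with covariates. If the plan is followed as written, the HAI comparison is unadjusted whatever was done with pet ownership elsewhere.

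Two things are at stake. The first is bias. With random allocation, differences in age or pet ownership would arise only by chance. Without it, nothing in the plan prevents a systematic difference, and the t-test would count that difference as an effect of the live dog. The second is precision. Over an age range of 2 to 18 years, part of the spread in how children interact with a dog is likely to come from age, and some perhaps from having an animal at home. The t-test leaves all of it in the error term.

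**Working it through.** **No figure to reproduce.** The documents give no sample-size calculation, power, alpha, SD or design effect. The 150 children in the Subjects table of the IRB record are a subject count without a power basis.

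**Where a covariate could enter, by analysis**

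| Analysis named | Applied to | Can hold pet ownership? | Said to? |
|---|---|---|---|
| Descriptive statistics | behaviour apart from sessions | as a breakdown | no |
| Poisson | bonding and in-session behaviour | yes | no |
| Independent t-test | HAI between groups | no | no |
| ANOVA | behaviour apart from sessions | as a further factor | no |

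The firm statement is therefore confined to the t-tests. For the other analyses the role of pet ownership is simply not stated.

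**A link between age and outcome in the plan itself.** "Therapy sessions lasted 30 to 45 minutes, depending on the age and ability of the participant". The 3-AAT ethogram measures frequency by tally. At the same rate of behaviour, 45 minutes of observation yields 45/30 = 1.5 times the tally of 30 minutes. The OHAIRE bond score is formed per 1-minute segment (0 to 36) and does not scale with session length in this way.

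**Precision (illustration).** Assumptions: two-sided alpha 0.05, equal groups, one independent value per child, and covariates that jointly explain R² = 0.10 to 0.30. Two sizes are shown: 75 per group (150 split equally) and 25 per group.

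- Equivalent gain in children = 1/(1 − R²) − 1. This is 1/0.90 − 1 = 11%, 1/0.80 − 1 = 25% and 1/0.70 − 1 = 43%.
- Smallest difference detectable with 80% power, in SD units = (1.960 + 0.842) × √(2/n) × √(1 − R²).
- Power for a difference of 0.5 SD (normal approximation) uses a residual SD of √(1 − R²).

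| | Unadjusted | R² 0.10 | R² 0.20 | R² 0.30 |
|---|---|---|---|---|
| Detectable difference, 75 per group | 0.457 | 0.434 | 0.409 | 0.383 |
| Power at 0.5 SD, 75 per group | 86.5% | 89.8% | 92.8% | 95.5% |
| Detectable difference, 25 per group | 0.792 | 0.752 | 0.709 | 0.663 |
| Power at 0.5 SD, 25 per group | 42.4% | 46.2% | 50.7% | 56.1% |

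**Bias (illustration).** Bias in SD units = (difference between groups in the proportion owning a pet) × (effect of ownership in SD).

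- Low end: 0.10 × 0.3 = 0.03 SD.
- High end: 0.30 × 0.5 = 0.15 SD.

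If the dog had no effect, the test statistic would be centred at bias/√(2/n) instead of zero. At 75 per group √(2/75) = 0.163, so the centre lies at 0.18 to 0.92, and the nominal 5% error rate becomes about 5.4% to 15.1%. At 25 per group the high end gives 8.3%.

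**The case against.** The strongest reply is that the sentence on pet ownership stands among the intake data and does not claim that ownership was a covariate in the HAI test. A reader might infer that the plan contradicts itself. The documents do not support that, because ownership may have entered the Poisson analysis, the ANOVA or the descriptive statistics. What stands is that its role is not stated and that the t-test cannot hold it.

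A reader might also infer that the HAI result is confounded. No baseline comparison is given, so confounding is possible but not shown. If allocation was in fact random, adjustment would mainly improve precision.

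It is tempting to add autism severity as a covariate already in hand, since the IRB Questionnaire lists "Childhood Autism Rating Scale- 2: 2 years to adulthood", which spans the study's ages. But that list is introduced by way of example. Children who already had a diagnosis could join on entering the program, and the timing of the score relative to sessions is not given. Complete pre-session severity data cannot be assumed.

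Nor can a loss of precision from the t-test be asserted for question 4 (in-session prosocial behaviour). The plan assigns in-session human behaviour to the Poisson analysis, although the sentence on the t-test null hypothesis also mentions human behaviours.

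Two further points are fair. The largest bias illustrated, 0.15 SD, is below the 0.20 that the plan labels small. And covariates chosen now are chosen after the data were collected. The first limits the size of the concern, and the second must be disclosed. Neither is a reason to report only an unadjusted comparison of groups whose allocation is not described.

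**Conclusion.** The point holds as an improvement to the HAI analysis. The role of pet ownership is not stated, the HAI t-test is unadjusted, and the plan describes no allocation method that would protect that test from imbalance in age or pet ownership.

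The size is not known from the documents. Under the assumed R² of 0.10 to 0.30, adjustment is worth 11% to 43% more children. Under the assumed imbalance and ownership effect, the bias is 0.03 to 0.15 SD. R², imbalance, ownership effect, equal split and group sizes are all assumptions. The figures also treat each child as one independent observation. Weekly sessions and optional re-enrolment make that doubtful, and covariates alone would not cure it.

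**What to change.** 1. State in which analysis pet ownership was used, for which outcome and in what role, and how children were allocated.
2. For HAI, report a group comparison with group, age and pet ownership in the model: a linear model for scores, and the already planned Poisson model for tally counts. Give the adjusted difference or rate ratio with its 95% CI beside the unadjusted t-test.
3. Say which model answers question 4 and put the same covariates in it.
4. Add a severity score only if one instrument is confirmed complete, and scored before sessions, for all children.
5. Label the adjusted analysis as added after data collection, since the Clinical Study Description reports the study as conducted through August 2024.

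Age is among the collected data, and pet ownership is reported as used. The cost is a re-run with about two degrees of freedom (one for age entered linearly, one for pet yes/no) and the weaker standing of a post hoc analysis.
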